Woebot user data provided to Stanford will be de-identified and linked via study ID to the study assessments we collect via RedCap Cloud and the data will not be shared outside of the Woebot and Stanford teams.

e) Indicate who will have access to the data or specimens (e.g., research team, sponsors, consultants) and describe levels of access control (e.g., restricted access for certain persons or groups, access to linked data or specimens).

The PD and co-investigator and the research team will have access to the study data. All data will be locked or password-protected or both.

f) If data or specimens will be coded, describe the method in which they will be coded so that study participants' identities cannot be readily ascertained from the code.

Each participant will be assigned a unique participant ID number, starting with 001 through 1000, to code data.

g) If data or specimens will be coded, indicate who will maintain the key to the code and describe how it will be protected against unauthorized access.

Title : Woebot for Substance Use Disorders Phase 2 RCT: Digitally Delivered Intervention for Reducing Problematic Substance Use (SU sIRB) Short name: Anchor Study

Approval Period: 03/17/2023 - 05/11/2023

IRB Modification 12/19/2022: The codes of names and ID numbers will be accessed by the research team only, stored securely in Qualtrics, REDCap Cloud, and/or a password protected file.

h) If you will be sharing data with others, describe how data will be transferred (e.g., courier, mail) or transmitted (e.g., file transfer software, file sharing, email). If transmitted via electronic networks, describe how you will secure the data while in transit. See <http://www.stanford.edu/group/security/securecomputing/> <http://www.stanford.edu/group/security/securecomputing/>. Additionally, if you will be using or sharing PHI see <https://uit.stanford.edu/security/hipaa> <https://uit.stanford.edu/security/hipaa>.

Coded data may be sent by secure email settings provided by Stanford, or through Stanford Medicine Box.

IRB Modification 12/19/2022: Woebot user data provided to Stanford will be coded and linked via study ID to the study assessments we collect via Qualtrics and REDCap Cloud, and the data will not be shared outside of the Woebot and Stanford teams.

i) How will you educate research staff to ensure they take appropriate measures to protect the privacy of participants and the confidentiality of data or specimens collected (e.g. conscious of oral and written communications, conducting insurance billing, and maintaining paper and electronic data)?

The research staff will all be HIPAA and CITI trained and compliant and supervised by [name].

12. Potential Conflict of Interest

Investigators are required to disclose any financial interests that "<https://researchcompliance.stanford.edu/eprotocol-coi>" target="_blank" reasonably appear to be related/li to this protocol.

Financial Interest Tasks

Investigators	Role	Potential COI?	Date Financial Interest Answered	Date OPACS Disclosure Submitted	COI Review Determination
[REDACTED]	[REDACTED]	[REDACTED]	[REDACTED]		[REDACTED]
[REDACTED]	[REDACTED]	[REDACTED]	[REDACTED]		[REDACTED]

13. Consent Background

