The purpose of this study is to test the efficacy of a mobile-application delivered substance use disorder intervention compared to an education only control group.

2. Study Procedures

Title : Woebot for Substance Use Disorders Phase 2 RCT: Digitally Delivered Intervention for Reducing Problematic Substance Use (SU sIRB) Short name: Anchor Study

Approval Period: 03/17/2023 - 05/11/2023

a) Please SUMMARIZE the research procedures, screening through closeout, which the human subject will undergo. Refer to sections in the protocol attached in section 16, BUT do not copy the clinical protocol. Be clear on what is to be done for research and what is part of standard of care.

Updated consent forms and HIPAA authorization will be uploaded before the start of recruitment. Ads, questionnaires, etc. will be uploaded for review before recruitment begins.

Recruitment will be a joint effort by Stanford University and Woebot Labs. Woebot may communicate the research opportunity through social media channels, and third party recruitment groups (e.g. Splash Clinical, Map & Story, Clara Health). The Stanford team may recruit through Qualtrics panels, ResearchMatch, listservs, and contact participants from previous research studies who are interested in future studies. Working with [name] research team at Stanford, the Woebot team will take part in mapping out message development for the intervention and Woebot's IT team will lead the app programming (including build and quality control/de-bugging). Woebot will collect user data via the Woebot app (automatic process), which will be provided to the Stanford team. The Woebot team will participate in disseminating the study findings via publications and presentations.

Participants from recruitment channels will go through and screening consent and eligibility screener, and if eligible, will be asked to participate in their randomized group for 8 weeks and answer questionnaires administered at the beginning, mid-intervention (4-week), end of intervention (8-week), and post intervention (12-week). Informed consent form will appear after screening eligible, and must be signed before the baseline survey can be accessed. Computer randomization will occur after the baseline survey, and instructions for their group will be sent out. Woebot will rely on Stanford University IRB for review of this study.

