Title : Woebot for Substance Use Disorders Phase 2 RCT: Digitally Delivered Intervention for Reducing Problematic Substance Use (SU sIRB) Short name: Anchor Study

Approval Period: 03/17/2023 - 05/11/2023

be provided after randomization.

A debrief document is attached in Section 16 and will be provided to participants after their study period. For those who complete the final survey, it'll be provided by email soon after. For those who do not complete the final survey, the information will be provided by email a month after the final survey (at 12-weeks) is due. This is to allow sufficient opportunity for the final survey to be completed before the timing of the final survey is considered "late". No participant will be given the debrief after the intervention period at 8-weeks since the study will also be observing sustained change post-intervention (between 8-weeks and 12-weeks).

d) State if audio or video recording will occur. Describe what will become of the recording after use, e.g., shown at scientific meetings, erased. Describe the final disposition of the recordings.

No audio or video recordings will occur.

e) Describe alternative procedures or courses of treatment, if any, that might be advantageous to the participant. Describe potential risks and benefits associated with these. Any standard treatment that is being withheld must be disclosed in the consent process and form. (i.e. standard-of-care drug, different interventional procedure, no procedure or treatment, palliative care, other research studies).

Alternative Treatments for SUDSs include in-person individual and group forms of psychotherapy as well as Alcoholics Anonymous and Narcotics Anonymous.

All alternative options will be provided if she/he/they wishes to engage in an alternative treatment rather than the proposed study. However, given that previous Woebot study results are promising, the proposed line of treatments would appear to be appropriate and acceptable interventions for SUDs.

No standard treatment is being withheld.

f) Will it be possible to continue the more (most) appropriate therapy for the participant(s) after the conclusion of the study?

[figure not shown]
Yes

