Please note that these items refer to alcohol or drug use and do not specify illicit drug use. The following measures will not be used in full, just a few selected items from these valid and reliable scales: Drug Abuse Screening Test (DAST-10), Michigan Alcohol Screening Test (MAST), Psychosis Screening Questionnaire (PSQ), and relevant demographic questions (i.e., age, pregnancy status, suicide or overdose within the past year). The study team will ask about alcohol and drug use broadly. Illicit drug use will not be specifically asked. The more sensitive items (such as suicide attempt and psychosis) will be grouped in a larger list of ineligibility criteria. Those who do not meet criteria will be welcomed to begin using the generic (non-SUD focused) Woebot and the website without restriction but will not be enrolled into the study. In addition, additional substance treatment resources will be provided.

j) Describe how you will be cognizant of other protocols in which participants might be enrolled. Please explain if participants will be enrolled in more than one study.
Consent form will ask whether the participant is currently enrolled in any additional studies.

k) Payment/reimbursement. Explain the amount and schedule of payment or reimbursement, if any, that will be paid for participation in the study. Substantiate that proposed payments are reasonable and commensurate with the expected contributions of participants and that they do not constitute undue pressure on participants to volunteer for the research study. Include provisions for prorating payment. See payment considerations

Phase II funding approved. For each of the 400 participants: \$25 for completing the baseline survey; \$25 for 4-week survey completion; \$25 for EOT (8-week) assessment completion; \$25 for the 12-week (30 days post EOT) assessment completion. Total amount possible per participant is \$100.

l) Costs. Please explain any costs that will be charged to the participant.

There will be no cost to participants.

m) Estimate the probable duration of the entire study. Also estimate the total time per participant for: (i) screening of participant; (ii) active participation in study; (iii) analysis of participant data.

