Potential Upset due to Survey Questions: Foreseeable risks to subjects include the possibility that some assessment questions and/or treatment procedures may be upsetting to subjects. Experience at Stanford with similar populations has indicated that the risk of emotional upset during the assessments is low and if it occurred, the upset would likely not be serious in nature and temporary. Such risks will be minimized by the thoughtful selection of questionnaires. Potential participants will also be informed that they may drop out of the study at any time and if requested, appropriate treatment referrals would then be given.

There is possible risk of discomfort from losing access to the study intervention at the end of the 8-week period.

Possible risks of Woebot: Woebot is not intended to replace standard of care and should not be used in place of standard treatment.

Neither of the intervention groups are crisis services.

The risks of the Economic well-being.

N/A

The risks of the Social well-being.

Potential loss of confidentiality.

Overall evaluation of Risk.

Low - innocuous procedures such as phlebotomy, urine or stool collection, no therapeutic agent, or safe therapeutic agent such as the use of an FDA approved drug or device.

b) If you are conducting international research, describe the qualifications/preparations that enable you to both estimate and minimize risks to participants. Provide an explanation as to why the research must be completed at this location and complete the [LINKFORINTERNATIONALREASEARCHFORM] International Research Form. If not applicable, enter N/A.

N/A

c) Describe the planned procedures for protecting against and minimizing all potential risks. Include the means for monitoring to detect hazards to the participant (and/or to a potential fetus if applicable). Include steps to minimize risks to the confidentiality of identifiable information.

Given that the research aims to enroll a low-treatment seeking population, we do not envisage that participation in the study will be associated with elevated risk. We are not assessing suicidal ideation in our questionnaires. During the eligibility screener, those who have had a suicide attempt within the past year will be excluded from the study. It is not feasible to confirm the responses by participants to the questionnaires in real time. However, some risk is always present in studies that involve human participants. Such risk may include the following:

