3. Risk of treatment avoidance due to engagement with either of the randomized interventions. In both interventions it is explicitly stated that the service should not be used in place of traditional treatment. [REDACTED]

4. Risk of suicide: Woebot informs the participant that it is not designed for crisis service. [REDACTED]

Additionally, if anyone is developing or indicating serious thoughts about suicide or harming themselves, it is best practice to call 9-1-1 and/or go to the nearest ER.

d) Explain the point at which the experiment will terminate. If appropriate, include the standards for the termination of the participation of the individual participant Also discuss plans for ensuring necessary medical or professional intervention in the event of adverse effects to the participants.

IRB Modification 12/19/2022: The study will terminate once the 3-month period with all 400 eligible participants has been completed and the analyses run and submitted for publication.

Participants can refuse to participate at any time.

When we learn of a participant's adverse event, the team will report the adverse event and may follow up with the participant for additional information. Resources will be offered. The EOT and 12-week surveys includes questions that assess for SAEs. More details about adverse events are in section e.

e) Data Safety and Monitoring Plan (DSMP). See guidance on Data Safety and Monitoring.

A Data and Safety Monitoring Plan (DSMP) is required for studies that present Medium or High risk to participants. (See Overall Evaluation of Risk above). If Low Risk, a DSMP may not be necessary. Multi-site Phase III clinical trials funded by NIH require the DSM Plan to have a Data Safety

Title : Woebot for Substance Use Disorders Phase 2 RCT: Digitally Delivered Intervention for Reducing Problematic Substance Use (SU sIRB) Short name: Anchor Study

Approval Period: 03/17/2023 - 05/11/2023

Monitoring Board or Committee (DSMC or DSMB). The FDA recommends that all multi-site clinical trials that involve interventions that have potential for greater than minimal risk to study participants also have a DSMB or DSMC.

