The role of the DSMC or DSMB is to ensure the safety of participants by analyzing pooled data from all sites, and to oversee the validity and integrity of the data. Depending on the degree of risk and the complexity of the protocol, monitoring may be performed by an independent committee, a board (DSMC/DSMB), a sponsor's Data Safety Committee (DSC), a Medical Monitor, a sponsor's safety officer, or by the Protocol Director (PD).

Describe the following:

What type of data and/or events will be reviewed under the monitoring plan, e.g. adverse events, protocol deviations, aggregate data?

The Data Safety and Monitoring Plan will include Woebot's standard safety net protocol as well as a Data Safety and Monitoring Board overseen by Stanford University. Woebot's Safety Net Procedures Study informed consent will state that Woebot is not a crisis program designed to address active suicidal ideation or overdose.

[REDACTED]

To make sure that we do not miss any cases, we over detect, rather than under detect. In addition, we periodically check the data for true/false positive rates. Adverse Events We do not anticipate that the use of the interventions will increase risk as outlined above. In addition, there is a limited capacity to detect adverse events (such as overdose, suicide attempt or hospitalization related to substance use or other) unless explicitly voluntarily reported by the participant. In the case Stanford University and / or Woebot Labs becomes aware of an adverse event, the appropriate protocol, approved by the DSMB and Stanford University's Institutional Review Board, will be immediately implemented. This includes immediate notification of the IRB, DSMB, and NIH, and an immediate convening of the DSMB to discuss requisite follow-up steps.

Identify who will be responsible for Data and Safety Monitoring for this study, e.g. Stanford Cancer Institute DSMC, an independent monitoring committee, the sponsor, Stanford investigators independent of the study, the PD, or other person(s).

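### SAE questions are stated for the week-8 and week-12 surveys but not for the paid 4-week survey; asking them there too would be a cheap gain in safety ascertainment

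*Protocol*

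**What the plan says.** Section 2a of the Protocol has participants in both groups "answer questionnaires administered at the beginning, mid-intervention (4-week), end of intervention (8-week), and post intervention (12-week"). Section 8k pays $25 "for 4-week survey completion", the same sum as for each of the other three surveys.

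On safety questions, section 9d says: "The EOT and 12-week surveys includes questions that assess for SAEs". It does not mention the 4-week survey, and it does not say that these two are the only surveys with such questions.

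Section 9e acknowledges "limited capacity to detect adverse events (such as overdose, suicide attempt or hospitalization related to substance use or other) unless explicitly voluntarily reported". Once Stanford or Woebot Labs learns of an event, an agreed procedure starts: "This includes immediate notification of the IRB, DSMB, and NIH, and an immediate convening of the DSMB to discuss requisite follow-up steps". Section 9e also describes an in-app safety net that is set to err towards over-detection, with periodic checks of true and false positives. Part of that text is redacted.

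The instrument list in section 11b contains no SAE measure and does not assign instruments to survey waves. The SAP does not mention adverse events. The questionnaires are not in the readable text; section 2a says: "Ads, questionnaires, etc. will be uploaded for review before recruitment begins".

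**The concern.** Three surveys follow baseline, and the text gives SAE questions to two of them. The one left out falls in the middle of the intervention period, goes to both arms and is already paid for. Two things follow if the 4-week survey does carry no SAE items.

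First, a participant who answers at week 4 and then stops answering is never asked about SAEs. The plan expects losses: section 1b reports high attrition in Phase I, and the SAP weights its models for retention at end of treatment and at the 1-month follow-up.

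Second, the notification procedure in section 9e starts only when the team becomes aware of an event. For an event that is neither volunteered nor otherwise detected, awareness has to wait for a survey that asks.

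There is also an issue of comparability by arm. The education content is not delivered through a conversational interface (section 1a), and the readable part of the safety net does not show that it reaches controls. The surveys are the only readable route by which both arms are asked the same SAE questions.

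**Working it through.** The documents give no figure on this point, so there is none to reproduce. The check is a reading of the text plus simple timing.

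**Inputs.** Survey weeks 4, 8 (EOT) and 12: sections 2a and 8k. SAE questions stated at weeks 8 and 12: section 9d. Planned sample 400: section 8a. Survey length 15 to 30 minutes: section 8m. Added time of 1 to 2 minutes for the SAE items: my assumption.

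**Lag to the first SAE question.** Take an event at week t, with 0 ≤ t ≤ 4, that is neither volunteered nor otherwise detected, and surveys answered on time.

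| Surveys answered | As written | With items at week 4 | Gain |
|---|---|---|---|
| 4 and 8 | 8 − t = 4 to 8 weeks | 4 − t = 0 to 4 weeks | 8 − 4 = 4 weeks |
| 4 and 12, not 8 | 12 − t = 8 to 12 weeks | 4 − t = 0 to 4 weeks | 12 − 4 = 8 weeks |
| 4 only | never asked | 4 − t = 0 to 4 weeks | asked once instead of never |
| 8 or 12, not 4 | 8 − t or 12 − t | unchanged | none |
| none | never asked | never asked | none |

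The gain requires that the participant completes the 4-week survey and discloses the event when asked. A participant who answers only at week 4 would be asked about the first four weeks, not about anything later.

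**Late surveys.** If the 4-week survey is d4 weeks late and the EOT survey d8 weeks late, the gain against EOT is (8 + d8 − t) − (4 + d4 − t) = 4 + d8 − d4 weeks. It is 4 weeks when d4 = d8 and zero when d4 = d8 + 4.

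**Capture or timing.** The recall window of the EOT questions is not readable. If they cover the full eight weeks, a participant who completes EOT is asked about early events anyway, and the week-4 items gain time only. For those who complete week 4 and neither later survey, the gain is in capture.

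**Burden.** 1/30 = 3.3% to 2/15 = 13.3% of a survey. If all 400 answer: 400 × 1 min = 6.7 hours to 400 × 2 min = 13.3 hours in total.

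**What cannot be computed.** The documents give neither an SAE rate nor the share completing week 4 but neither later survey. Any number of people or events would be a multiple of a guess.

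**The case against.** The strongest reply is that asking at the end of treatment and the end of the study is a legitimate choice that breaks nothing in the plan. Section 9a rates overall risk as Low, and the form says that a monitoring plan may then be unnecessary. The trial nevertheless has a DSMB, SAE questions at two waves and immediate notification. Past-year suicide attempt and opioid overdose are exclusions (section 8h), retention strategies from the W-C19 study will be reused (section 3a), and the safety net leans towards over-detection. No readable stopping rule depends on SAE counts, so the decision that earlier knowledge would change is not shown. All of this stands. It narrows the group affected, but none of it asks both arms about early events at week 4.

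Three stronger readings are tempting, and the documents do not support them.

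- A reader might infer that the 4-week survey definitely lacks SAE items, or that the Protocol contradicts itself. Section 9d names two surveys without excluding the third, the questionnaires are separate uploads, and nearby safety text is redacted.
- A reader might take "It is not feasible to confirm the responses by participants to the questionnaires in real time" in section 9c to mean that answers are reviewed slowly. The sentence follows the one on screening out recent suicide attempts and most naturally concerns verifying what people report. It does not say how soon staff read the answers.
- A reader might infer that early events are lost for everyone. For EOT completers that depends on a recall window that cannot be read.

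**Conclusion.** The point holds as a cheap improvement to safety ascertainment, not as an error. On the text as written, a participant who completes week 4 but neither later survey is never asked about SAEs. An early event that is neither volunteered nor otherwise detected is first asked about at week 8 when week 4 was available. The gain is about 4 weeks, given on-time surveys, completion of both the 4-week and EOT surveys, and disclosure when asked. The size of the affected group is unknown and may be small. The conclusion rests on the 4-week survey not already carrying the items; if it does, only a clarifying sentence is needed.

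**What to change.** Add the SAE items used at EOT and 12 weeks to the 4-week survey in both arms, and name all three surveys in section 9d. If the items are already there, say so in that section. In the report, give the number asked at each wave by arm next to the SAEs, and keep survey-solicited events separate from those volunteered or detected in the app, since the last route may not be equally open to both arms.

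The cost is an IRB modification and a minute or two (assumed) per participant. The same event may be reported at two waves, so reports must be matched. Some notifications under section 9e will come earlier, and events that would never have been asked about will add to them. The documents do not make clear whether enrolment has begun. If it has, week-4 ascertainment will differ between earlier and later enrollees, and the report should give the date of the change. People who leave before week 4 are still not reached.
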